3.1. Study design

Randomized triple-blinded multicentric clinical trial, conducted in parallel, with two arms:

The trial will be performed with health care workers (Physicians, Nurses, Respiratory therapists, or nurse assistants) free of SARS-CoV-2 infection prior, recent or at the time of the inclusion and who directly care for confirmed or suspected cases of COVID-19 in the emergency room, general COVID wards or intensive care units. A screening at baseline will be carried out in order to evaluate for eligibility by performing: SARS-CoV-2 RT-PCR, SARS-CoV-2 IgG antibodies, as well as, hemogram, creatinine, serum phosphorus, AST, ALT, ELISA for HIV, surface Hepatitis B antigen antibodies, qualitative pregnancy test (b-HCG). Once

eligibility is verified participants will be randomly assigned to either an intervention or a control group.

The interventions consists in the administration of Tenofovir/ Emtricitabine (300 mg / 200 mg daily during 60 days) + Personal Protective Equipment (PPE) and the control consists in the administration of placebo (1 tablet daily during 60 days) + Personal Protective Equipment (PPE)

All participants will have PPE recommended for the preventions of COVID-19 by the WHO which include mayo dress, nonfluid long sleeve gown, ocular protection with goggles, face shield or visor and surgical mask in procedures that do not aerosolize. N-95 respirators are required for procedure that generate aerosols. For detailed description see Table 2.

The re-use of N-95 respirators will be allowed according to CDC and WHO guidelines. This taking into consideration the shortage of supplies for the actual situation. The N-95 continuous use will be for 8 hours and the N-95 intermittent use will be allowed up to 5 times with the precaution of storage in a paper and plastic bag label them with the participant name and placed them in a plastic recipient at the end of shifts(48).

After baseline evaluation and confirming eligibility an initial visit and 4 follow up visits at day 20, 40, 60, 75 days will be carried out. See Table 1 and Graph 1.

In the case of presenting COVID-19 related symptoms at any time after enrolling a SARS-CoV2 RT-PCR will be performed between day 1 to 5 of the onset of symptoms and will be repeated it after 72 hours in case that the first one is negative. In the case of having any positive SARS-CoV2 RT-PCR or SARS-CoV2 IgG SARS-CoV2 infection will be confirmed and the intervention will be suspended.

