3.6. Procedures

In table 1. Detailed follow up evaluations are described.

Table 1. Description of the evaluations to be done during the trial.

Follow up table				
Day	General activity	Specific activity	Responsible	Result
0	Base line diagnoses	Initial Clinical evaluation	Medical doctor of the study	Evaluating inclusion and exclusion criteria. Signing informed consent form
		Blood samples	Nurse Lab tech	Laboratory report: hemogram, creatinine, phosphorus, AST, ALT HIV ELISA, HB Surface antigen antibodies
		SARS-CoV-2 RT-PCR sampling	Respiratory therapist or nurse	Result of SARS-CoV-2 RT-PCR
		SARS-CoV-2 IgM and IgG antibodies	Nurse Lab tech	Result of IgM and IgG antibodies
		b-HCG sampling in women	Nurse Lab tech	Report of b-HCG
20	Visit 1	Clinical evaluation	Medical doctor of the study	Clinical record and eCRF for clinical evaluation, adherence, and adverse events

40	Visit 2	Blood sample for: SARS-CoV2 IgM, IgG antibodies and blood chemistry	Nurse Lab tech	Laboratory report of SARS-CoV2 IgM, IgG antibodies and creatinine
		Clinical evaluation	Medical doctor of the study	Clinical record and eCRF for clinical evaluation, adherence, and adverse events
60	Visit 3	Blood samples	Nurse Lab tech	hemogram, creatinine, phosphorus, AST, ALT HIV ELISA, HB Surface antigen antibodies b- HCG in women
		SARS-CoV-2 RT-PCR sampling	Respiratory therapist	Result of SARS-CoV-2 RT-PCR
		Clinical evaluation	Medical doctor of the study	Clinical record and eCRF for clinical evaluation, adherence, and adverse events
75	Visit 4	Blood samples	Nurse Lab tech	Laboratory report of SARS-CoV2 IgG
		Clinical evaluation	Medical doctor of the study	Clinical record and eCRF for clinical evaluation,
		End of follow up and communication to study subject	Clinical coordinator	Minutes

During follow up to any participant who develop COVID-19 related symptoms at any time after randomization given by two or more of the following: Body temperature higher than 38 Celsius, cough of recent onset (in the previous 10 days), dyspnea,odynophagia, malaise, fatigue, acute diarrheal disease, ageusia, dysgeusia, anosmia or hyposmia, an RT-PCR will be performed within the next 5 days and will be repeat it if the result is negative and the symptoms persist. This RT-PCR will be performed at every of the centers of the study and will request the patient the immediate report of the symptoms through an app or via phone call. In case of a positive RT-PCR the infection

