will be confirmed. While confirmation RT-PCR arrives, the participant will not quit taking the intervention. In that scenario, the intervention will only be suspended in the case of a highly suspected case or severe case requiring hospitalization.

In case the infection is ruled out in the follow up, the participant will continue the interventions and follow up scheduled, according to graph 1.

With regards to diagnostic testing during follow up as shown in table 1. IgG antibodies will be done at visit 2 and 4 (40 days from initially taking the intervention and 15 day after finalizing it). This considering volunteer that might acquire the infection in the last days of the pharmacological intervention. Moreover, at day 60, last of the intervention, an RT-PCR will be performed to all participants. This in order to detect participants who develop asymptomatic infection. The research group is aware that this follow up will not identify a 100% of the asymptomatic infection for the low sensitivity of testing in this scenario, approximately 30 to 40% (46,47), yet it will be done in both arms.

Importantly, for the covid-19 emergency, clinical follow up, adverse event reporting and adherence reporting could be done online.

Personal Protective Equipment

All volunteers will be using the following personal protective equipment. This based on the guidelines of the WHO (23). See table 2.

Table 2. Use of PPE by study volunteers.

Area	Health care personnel or patients	Activity	Type of PPE or activity
Emergency room, general COVID wards or intensive care units	Health care workers	Direct contact with the patient of non-aerosol generating procedures.	Surgical mask Visor or glasses. Long sleeve gown Nonsterile gloves.
		Direct contact with the patient and aerosol generating procedures.	N95 respirator Visor or glasses. Long sleeve gown Nonsterile gloves. May dress

			under the robe that is removed at the end of the shift
Other areas of transit (hallways or waiting rooms)	All personnel including health care workers	Any activity that does not involve contact shorter than 2 meters in distance between people	Surgical mask

Adapted from: Rational use of personal protective equipment for coronavirus disease 2019 (COVID-19). Interim guidance 27 February 2020. World Health Organization. (23)

*Health care worker: person in whose activity directly care a contact, suspected, or confirmed case of COVID-19.

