In a randomized, double-blind, placebo-controlled trial of PrEP in African women, Mugo NR, and colleagues (78) evaluated the effect of TDF/FTC on pregnancy for HIV-uninfected women. Differences in the incidence of pregnancy, delivery outcomes, and infant growth were not statistically different for women who received PrEP with TDF alone, or combination of FTC + TDF compared to placebo at conception. Considering that PrEP was discontinued when pregnancy was detected and that the confidence intervals for delivery outcomes were wide, the authors did not commit to making definitive statements about the safety of PrEP in the period of periconception (78).

For the above reasons, if any volunteer presents a pregnancy at the end of the intervention period, a specific Informed Consent Form will be filled out to carry out a follow-up during the pregnancy.

4. Statistical analysis plan

Initially, a descriptive analysis of the information will be made, and measures of central tendency and dispersion will be reported according to the type of variables. In this phase, the similarity between the groups of the experiment will be evaluated and it will be calculated if there are differences in the groups due to chance.

Primary outcome

Taking into account that this study is a pragmatic clinical experiment, which will evaluate effectiveness, an intention-to-treat analysis will be carried out, to solve the main objective, the proportion of incidence of SARS-CoV-2 infection in each group will be determined at the day 75 post-randomization, estimated as the cumulative incidence of infection using the Kaplan Meier method.

Exposure of interest: Prophylaxis with TDF/FTC plus EPP vs placebo plus EPP.

Primary outcome: SARS CoV2 infection

Zero follow-up time (registration time in the registry): the time that the volunteer is randomized to the study interventions.

Follow-up time: All individuals have a follow-up until they present the primary outcome, or meet any of the withdrawal criteria, or up to 75 days after the zero follow-up time, if they do not present the outcome.

Event: SARS-CoV-2 infection.

Censorship: censorship occurs when the outcome is not presented, the two types of censorship will be: administrative censorship 75 days after randomization, or censorship for compliance with any of the criteria for withdrawal from the study, or loss of follow-up.

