The hazard ratio will be estimated by comparing the risk of infection in the intervention group (TDF/FTC + EPP), with the risk in the control group (placebo + EPP), with a confidence interval of 95 %, using a univariate Cox regression model.

If necessary, adjustment will be made for variables that may affect the occurrence of the primary outcome and that are not balanced between the intervention group and the placebo group; The need for adjustment with an OR greater than 1.5 will be considered for dichotomous categorical

variables, such as sex; or if there are differences between the groups greater than 0.25 of the standard deviation for continuous variables such as age, adherence to pharmacological intervention or EPP, and hours of exposure to the COVID area. For the calculation of the adjusted hazard ratio, a multivariate Cox proportional hazards model will be used, if the proportionality assumption is met, or an extended Cox model if this assumption is not met.

For secondary outcomes

-The proportion of incidence of total adverse effects in each group will be determined at day 60 after randomization, estimated as the cumulative incidence using the Kaplan Meier method.

The hazard ratio ("Hazard Ratio") will be estimated by comparing the risk of adverse events in the intervention group (TDF/FTC + EPP), with the risk in the control group (placebo + EPP), with a confidence interval of 95%, using a univariate Cox regression model.

Additionally, the same analysis will be performed for serious adverse events.

- The proportion of incidence of discontinuation of the intervention in each group, for any reason, will be determined at day 60 after randomization, estimated as the cumulative incidence using the Kaplan Meier method.

The hazard ratio will be estimated by comparing the discontinuation of the intervention in the intervention group (TDF/FTC + EPP), with the risk in the control group (placebo + EPP), with a confidence interval of 95 %, using a univariate Cox regression model.

- It will be determined as the difference in the mean or median (according to the distribution of the data) of the percentage in which the individuals were adherent

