Telephone contact potential volunteers		X							Registration with participants interested in being included	Record of execution of the procedure and database in Excel.
Informed consent		X							Signed informed consents	Database of study subjects recruited
Clinical CRF history		X	X	X	X	X			Clinical History of the study subject	Clinical CRF Registry
Clinical Assessment		X	X	X	X	X			Clinical History of the study subject	Clinical CRF Registry
Supervised first dose of drug administration		x							Confirmation of taking at least 1 dose of TDF/FTC or placebo	Drug dispensing registration document
Taking of RT-PCR for SARS-CoV-2		X			X				Positive or negative diagnostic test result	Laboratory report
Antibody IgG - IgM SARS - CoV-2 testing		X		x		x			Positive or negative diagnostic test result	Laboratory report
Sampling for CBC, Creatinine, AST, ALT, P, HIV ELISA, Acs anti HBsAg and		X		X		X			Results of liver, kidney, hematological, electrolyte function tests and pregnancy status in the	Laboratory report

Beta HCG in women									case of participating women.	
Verification of eligibility criteria		X							Determination of the inclusion or not of the participant	Check list
Randomization		X							Random Assignments to Intervention or Placebo	Database
CRF Adverse Events Registry			X	X	X	X			History of adverse events	CRF registration document Adverse event
Finish follow-up and communication to the study subject							X		Formal follow-up completion record	Completion certificate document
Systematization and organization of data							X		Office registry refined with data extracted from the clinical trial	Systematized database
Results analysis								X	Outcome estimates, statistical associations, causality inferences and risks of bias and limitations	Document with results, tables, graphs and data of the study
Communication and publication of results and conclusions.								X	National and international communication of the results and	Two articles of scientific publication, report of results and recommendation

									conclusions of the study	ns of the researchers
--	--	--	--	--	--	--	--	--	-----------------------------	--------------------------

9. Budget

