Diastolic blood pressure	Quantitative/discrete	Diastolic blood pressure	Diastolic blood pressure in mmHg
Creatinine	Quantitative/continuous	Serum creatinine concentration (mg/dl).	Serum creatinine concentration (mg/dl).
Creatinine rise	Qualitative/nominal	Severity of creatinine rise	0-Normal 1-Grado 1 2-Grado 2 3-Grado 3 4-Grado 4
IgG for SARS-CoV-2	Qualitative/dichotomous	Result of serology test for SARS-CoV-2 (only for follow-up 2)	0- Negative 1- Positive
Data to be collected in follow-up 3			
Platelets	Quantitative/discrete	Number of platelets in complete blood count (CBC)	Number of platelets per microliter (Cels/ μ l).
Thrombocytopenia	Qualitative/nominal	Severity of thrombocytopenia	0-Normal 1-Grade 1 2-Grade 2 3-Grade 3 4-Grade 4
Hemoglobin (Hb)	Qualitative/continuous	Hemoglobin concentration in CBC	Hb (g/dl).
Anemia	Qualitative/nominal	Classification of severity of anemia	0-Normal 1-Grade 1 2-Grade 2 3-Grade 3 4-Grade 4
Lymphocytes	Quantitative/discrete	Number of lymphocytes in complete blood count (CBC)	Number of lymphocytes per microliter (Cels/ μ l).
Lymphopenia	Qualitative/nominal	Classification of severity of lymphopenia	0-Normal 1-Grade 1 2-Grade 2 3-Grade 3 4-Grade 4
Neutrophils	Quantitative/discrete	Number of neutrophils in complete blood count (CBC)	Number of neutrophils per microliter (Cels/ μ l).
Neutropenia	Qualitative/nominal	Classification of severity of neutropenia	0-Normal 1-Grade 1 2-Grade 2 3-Grade 3 4-Grade 4
Aspartate aminotransferase (AST)	Quantitative/continuous	AST concentration in international units per liter (UI/l)	AST (UI/l).
Aspartate aminotransferase elevation	Qualitative/nominal	Severity of elevation of AST	0-Normal 1-Grade 1 2-Grade 2 3-Grade 3 4-Grade 4
Alanine aminotransferase (ALT)	Quantitative/continuous	ALT concentration in international units per liter (UI/l)	ALT (UI/l).
Alanine aminotransferase elevation	Qualitative/nominal	Severity of elevation of ALT	0-Normal 1-Grade 1 2-Grade 2 3-Grade 3 4-Grade 4

Pregnancy test	Qualitative/dichotomous	Applicable only to women. Result of quantitative serum Beta-HCG test regarding upper reference value for non-pregnant women.	0- Negative 1- Positive
RT-PCR SARS-CoV-2	Qualitative/dichotomous	Detection of SARS-CoV-2 by RT-PCR de	0- Undetectable 1- Detectable
Data to be collected only in Follow-up 4			
Follow-up date	Quantitative/continuous	Follow-up date	Day/month/year

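### The adverse event proportion is read at exactly day 60 after randomization, the day the only scheduled post-baseline blood count and transaminase sample is due, so results from late draws are left out of it

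*Combined protocol and SAP*

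**What the plan says.** Section 4 (Statistical analysis plan), secondary outcomes: "The proportion of incidence of total adverse effects in each group will be determined at day 60 after randomization", as a Kaplan-Meier cumulative incidence, with the same analysis for serious events. A separate paragraph says that a hazard ratio "will be estimated by comparing the risk of adverse events in the intervention group (TDF/FTC + EPP") against placebo by univariate Cox regression. That paragraph gives no time limit. Under the primary outcome, time zero is "the time that the volunteer is randomized to the study interventions", and infection is followed to day 75.

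Section 3.1 plans "an initial visit and 4 follow up visits at day 20, 40, 60, 75 days will be carried out". No window around these days is stated.

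Safety sampling after baseline is described as follows:

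- **Table 1 (section 3.6).** Day 40 yields "Laboratory report of SARS-CoV2 IgM, IgG antibodies and creatinine". Day 60 has blood count, creatinine, phosphorus and transaminases. Day 75 has SARS-CoV-2 IgG only, and its clinical evaluation does not list adverse events.
- **Budget (section 9.1).** Follow-up 2 has creatinine and antibodies. A later item covers creatinine, blood count, transaminases and an RT-PCR for everyone, which matches visit 3.
- **Appendix 3.** Blood count components, AST and ALT stand under "Data to be collected in follow-up 3". Creatinine is collected at follow-ups 2 and 3. Adverse event fields cover follow-ups 1 to 3, and the follow-up 4 block has none.
- **Table 6.** The row that begins "Sampling for CBC, Creatinine, AST, ALT, P, HIV ELISA, Acs anti HBsAg and" is marked at recruitment, visit 2 and visit 4, but not at visit 3. The adverse event registry is marked at all four visits.

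Section 6.1 counts an abnormal laboratory finding as an adverse event. Section 6.2 records the date of the event but gives no rule for dating one found on a blood test.

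**The concern.** The cut-off and the main safety sample fall on the same nominal day. A Kaplan-Meier estimate at day 60 includes events dated up to and including day 60. A participant sampled on day 61 is, for that estimate, still at risk and event-free, whatever the sample later shows.

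Some lateness is plausible. Section 3.6.4 releases the bottle through telephone calls after randomization, and Appendix 3 records the randomization date and the product start date separately. Section 3.6 counts the day-40 visit from first intake, whereas the analysis clock starts at randomization.

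At stake is the absolute incidence of hepatic and hematologic abnormalities, and of creatinine abnormalities first seen at visit 3. Section 4.1 decides against a data monitoring committee, so the final analysis is the planned comparison of safety between arms.

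**Working it through.** The plan states no figure for the timing of adverse events, so there is none to reproduce. The one plan figure used below is 475 per arm (section 3.4).

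**1. Effect on the proportion.** Let q be the true proportion of participants with a laboratory event first seen on the visit 3 panel, and L the share of visit 3 draws after day 60. With events dated at the draw, and lateness unrelated to the result:

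day-60 proportion = q × (1 − L)

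**2. Illustration.** Section 5.1.1 cites a pre-exposure prophylaxis trial with neutropenia of 15% (grade 1 or 2) plus 4% (grade 3 or 4) on TDF/FTC, and 12% plus 2% on placebo. Summed, that is 19% against 14%. The trial ran 36 months, so these rates only show the mechanism. L is assumed.

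| L | TDF/FTC | Placebo | Difference (points) | Ratio | Participants missed: 475 × (0.19 + 0.14) × L |
|---|---|---|---|---|---|
| 0 | 19.0% | 14.0% | 5.0 | 1.36 | 0 |
| 10% | 17.1% | 12.6% | 4.5 | 1.36 | 15.7 |
| 30% | 13.3% | 9.8% | 3.5 | 1.36 | 47.0 |
| 50% | 9.5% | 7.0% | 2.5 | 1.36 | 78.4 |

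At a lower assumed rate of 5% in both arms, the number missed is 475 × 0.10 × L: about 5 at L = 10% and 24 at L = 50%.

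**3. What L might be.** The documents do not say. If draws spread evenly over days 57 to 63, 3 of 7 days are late (43%), and 19% reads as 0.19 × 4/7 = 10.9%. Over days 53 to 67, 7 of 15 days are late (47%), and it reads as 0.19 × 8/15 = 10.1%. A simulation gave 0.109 and 0.101, and 0.19 in both cases once the horizon was moved to day 67 or day 75. If every draw is on or before day 60, L = 0 and nothing is lost.

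**4. Which clock.**

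- If the first tablet is taken on day d after randomization, the 60th uninterrupted daily tablet falls on day d + 59. With d of 2 or more, the last dose itself is after the cut.
- Against that, Table 1's day 0 is the baseline evaluation, and section 3.6.2 confirms eligibility and randomizes 24 to 48 hours later. Counted from Table 1's day 0, visit 3 falls 60 − 2 = 58 to 60 − 1 = 59 days after randomization, inside the cut.

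The documents support either reading.

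**5. Under Table 6.** The visit 2 panel (day 40) lies inside the window. Anything first seen on the visit 4 panel (day 75) lies outside it.

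**The case against.** Day 60 is a coherent horizon. It equals the treatment period, matches the horizon of the discontinuation analysis, and coincides with "at day 60, last of the intervention, an RT-PCR will be performed to all participants". An event dated day 60 counts, and no document says that visits will run late. This stands: the loss is conditional, and its size is an assumption.

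Four stronger readings are tempting, and the documents do not support them.

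- **That half or nearly all laboratory events are lost.** No late share is documented. Even scatter over a plausible window gives 43% to 47%. Adding a one- or two-day delay to the 57 to 63 spread gives 4/7 to 5/7 (57% to 71%), which is still not nearly all. The Table 1 clock could give zero.
- **That the comparison between arms is biased and harm therefore under-estimated.** Under blinding there is no stated reason for lateness to differ by arm, and equal lateness leaves the ratio unchanged. The Cox paragraph carries no day-60 limit, so late events may still enter the hazard ratio.
- **That no safety blood test falls clearly inside the window.** Creatinine is drawn at day 40 in every version of the schedule, and Table 6 places a full panel there too.
- **That no analysis would use events recorded at visit 4.** They fall outside the day-60 proportion, but with no horizon stated for the Cox model their exclusion from it is not established.

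Symptomatic events are captured by the diary and at visits 1 to 3, so the panel date does not affect them. A participant already counted for an earlier event also stays in the total proportion. The figures above therefore describe laboratory events taken alone, and the effect on the total is smaller.

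**Conclusion.** The point holds as a limited but avoidable under-count. Under Table 1, the budget and Appendix 3, the only scheduled post-baseline blood count, AST and ALT are due on the cut-off day. Any sample drawn later contributes nothing to the day-60 proportion. Absolute incidence of events first seen on that panel, and the absolute difference between arms, both fall by the share of late draws: 10% to 50% if 10% to 50% are late, and zero if none are.

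This assumes that laboratory events are dated at the draw and that lateness is unrelated to the result. The ratio is unbiased if lateness is equal by arm. The horizon of the hazard ratio is unspecified, so it may not describe the same period as the proportion reported beside it.

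Two inconsistencies in the documents add to this. Table 6 disagrees with Table 1 on where the panel falls. Table 6 also has adverse events recorded at visit 4, while Table 1 and the Appendix 3 follow-up 4 block do not.

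**What to change.** In section 4, define the horizon for adverse and serious adverse events so that it includes results of the actual visit 3 sample, whatever its date. Alternatively, run it to visit 4 (about day 75) and report an on-treatment summary beside it. Apply the same horizon to the Kaplan-Meier proportion and to the hazard ratio. State the visit 3 window, the day from which visits are counted, and how a laboratory event is dated.

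Add adverse event fields to the follow-up 4 block of Appendix 3. Reconcile Table 6 (panel at visits 2 and 4, adverse event registry at visit 4) with Table 1 (panel at visit 3, no adverse event entry at day 75).

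The cost is analysis plan wording and a few form fields at a visit that already takes place. The downside is small: some off-drug days enter the window, about 75 − 60 = 15 if it runs to visit 4. Under Table 1, running to visit 4 adds no further safety blood tests. Its gain is that late visit 3 results and events after the end of treatment are counted.

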months of follow-up was similar in all study groups. There were no statistically significant differences in the frequency of deaths, serious adverse events, or serum creatinine and phosphorus abnormalities in the study arms. Neutropenia was seen more frequently in the TDF/FTC arm (15% with a grade 1 or 2 event, 4% with a grade 3 or 4 event), but not in the TDF arm (12% with a grade 1/2, 2% grade 3/4), compared to placebo (12% grade 1/2, 2% grade 3/4). The study medication was well tolerated, with a moderate increase in reports of gastrointestinal side effects and fatigue in the two active arms compared to the placebo arm, mainly during the first month of administration (77,95)

Retention was 96% or greater during the study period. Study medication interruptions for safety-related reasons accounted for less than 1% of the total follow-up time: 0.6% in the TDF group, 0.7% in the TDF-FTC group, and 0.6% in the placebo group. (77.95)

The iPrEX study enrolled 1603 volunteers, of whom 1,225 chose to take PrEP. Reported symptoms peaked in the first month, with 39% potentially related to PrEP compared to 22% at baseline. Symptoms largely resolved within 3 months. Symptoms related to the digestive tract in the first 4 weeks were inversely associated with adherence at 4 weeks (OR = 0.47, 95% CI 0.23 to 0.96). Reports of gastrointestinal symptoms were associated with 7% (95% CI, 4% -11%) of suboptimal adherence in this cohort (96).

In this study, PrEP delivery was discontinued during the study in 56 (5%) volunteers due to "adverse effects." The study volunteer or medical staff could initiate interruptions. The interruption was temporary for 22 volunteers, the combined duration of these temporary interruptions totaled 10 person-years, a reduction of 0.6% (10 person-years from a possible 1784 person-years) in the total possible person-years. The discontinuation was permanent for 34 volunteers and decreased the total possible use of PrEP in 35 person years, 2.9% of the possible use in the cohort. The most common adverse effects cited for non-dispensing were nausea, abdominal pain (0.9% possible use), diarrhea (0.4%), and skin problems / itching, pain in head and flatulence (0.3% each (96).

- Laboratory abnormalities

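### The only between-arm adverse-event contrast with a confidence interval is one 60-day Cox hazard ratio, with no proportionality check, although the cited evidence places the excess symptoms mainly in month one

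*Combined protocol and SAP*

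**What the plan says.** Section 4, under secondary outcomes, plans two measures for adverse events. The first is absolute, by arm: "The proportion of incidence of total adverse effects in each group will be determined at day 60 after randomization, estimated as the cumulative incidence" by Kaplan-Meier. The second is a univariate Cox hazard ratio with a 95% confidence interval, which "will be estimated by comparing the risk of adverse events in the intervention group" with the risk in the control group. Serious events are handled alike: "Additionally, the same analysis will be performed for serious adverse events". No difference or ratio of the day-60 incidences is planned.

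Proportionality is mentioned once in section 4, for the adjusted hazard ratio of the primary outcome: a multivariate Cox model "if the proportionality assumption is met, or an extended Cox model if this assumption is not met". Nothing similar is written for the adverse-event models.

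On timing, section 5.1.1 cites a placebo-controlled PrEP trial in couples. It found a moderate increase in gastrointestinal effects and fatigue "in the two active arms compared to the placebo arm, mainly during the first month of administration". For an open-label PrEP cohort the same section says "Reported symptoms peaked in the first month, with 39% potentially related to PrEP compared to 22% at baseline" and "Symptoms largely resolved within 3 months".

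**The concern.** A Cox model with treatment as its only term summarises the whole follow-up in one ratio. If the drug raises the hazard of a first adverse event in month one and much less in month two, no single ratio describes both months. The estimate falls between the early and late ratios, and the early one is understated. The protocol's own evidence gives a reason to expect this pattern for the commonest drug effects, yet the proportionality check is reserved for another outcome.

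Safety is named in the general objective, and section 4.1 explains that there is no data monitoring committee, so the final comparison carries much of the safety inference. Section 5.1.1 also links early digestive symptoms to poorer adherence at 4 weeks, so first-month tolerability matters for interpreting effectiveness too.

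**Working it through.** **The plan's own figure.** The documents state no expected rate, hazard ratio or power for adverse events. The only computed design figure is 429 per arm for the primary outcome. It reproduces: (1.960 + 0.842)² × (0.10×0.90 + 0.05×0.95) / 0.05² gives 432 (435 with pooled variance). It does not bear on this point.

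**Inputs.** From the documents: 475 per arm, 10% loss, 60 days of dosing. Assumed: risk of a first adverse event by day 28 of 22% on placebo and 30% on drug; hazards constant within days 0-28 and 29-60. The 22% is borrowed from the open-label cohort's baseline figure, only as a plausible level.

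**Early hazards.** −ln(0.78)/28 = 0.00887 per day on placebo and −ln(0.70)/28 = 0.01274 on drug. The early hazard ratio is 0.01274/0.00887 = 1.44.

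**The 60-day hazard ratio if the effect stops at day 28.** Let the background hazard after day 28 be f times the early placebo hazard. Day-60 risks are 1 − exp(−28·h₀ − 32·f·h₀) on placebo and 1 − exp(−28·h₁ − 32·f·h₀) on drug. With a true ratio of 1 in the second period, the Cox log hazard ratio is close to ln(1.436) = 0.362 times the share of first events occurring by day 28. That share is (0.22 + 0.30) divided by the sum of the two day-60 risks.

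| f | Day-60 risk, placebo / drug | Difference (8.0 points at day 28) | Share of events by day 28 | 60-day HR |
|---|---|---|---|---|
| 1 | 41.3% / 47.3% | 6.0 | 0.587 | exp(0.213) = 1.24 |
| 0.5 | 32.3% / 39.3% | 6.9 | 0.726 | exp(0.263) = 1.30 |
| 0.25 | 27.3% / 34.8% | 7.5 | 0.837 | exp(0.303) = 1.35 |

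Solving the large-sample Cox score equation gives the same hazard ratios. Moving the split to day 30 gives 1.25, 1.31 and 1.36.

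**Power.** Simulation with 475 per arm, 10% uniform loss, two-sided 5% and 3,000 trials per row:

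| 28-day risks | f | Effect after day 28 | 60-day Cox | KM difference, day 28 | KM difference, day 60 |
|---|---|---|---|---|---|
| 22% / 30% | 1 | none | 0.57 | 0.80 | 0.45 |
| 22% / 30% | 0.5 | none | 0.66 | 0.79 | 0.58 |
| 22% / 30% | 0.25 | none | 0.73 | 0.80 | 0.69 |
| 22% / 30% | 1 | half the log-HR (HR 1.20) | 0.82 | 0.79 | 0.75 |
| 22% / 30% | 1 | all (HR 1.44) | 0.97 | 0.82 | 0.96 |
| 22% / 27% | 1 | none | 0.26 | 0.42 | 0.20 |
| 22% / 27% | 1 | half the log-HR | 0.45 | 0.44 | 0.40 |

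The day-28 column should be equal across rows with the same 28-day risks; its variation is simulation error.

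**The case against.** The strongest reply is that the plan already gives the size of the harm without assuming proportionality, through Kaplan-Meier incidence by arm at day 60. This stands. In the scenarios above, the day-60 difference keeps 6.0 to 7.5 of the 8.0 points seen at day 28. A reader might infer that the hazard ratio averages the harm away. It does not: first events cluster early, so the Cox estimate is weighted toward the period of harm and stays above 1.

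A reader might also treat 39% against 22% as the expected drug-placebo contrast. It compares month one with baseline in an open-label cohort and says nothing direct about placebo.

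Nor do the documents show that the effect ends at day 28. Symptoms resolved largely within 3 months, which is longer than the 60-day window, and resolution of existing symptoms is not the same as timing of first events. The loss of power disappears once half of the log hazard ratio persists.

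The endpoint is total adverse events, and section 5.1.1 cites a meta-analysis with no overall difference from placebo (OR 1.01, 95% CI 0.99 to 1.03). That weakens any claim of a known effect on this endpoint, though it does not exclude an early excess in some symptoms.

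Finally, a month-one focus alone would be wrong. In Table 1 post-baseline creatinine is drawn at days 40 and 60, and hemogram, phosphorus and transaminases at day 60, so scheduled laboratory abnormalities appear only in month two. Replacing Cox with the day-60 difference would also lose power when the effect stops early (0.45 against 0.57).

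What remains is that the only contrast with an interval rests on an unchecked assumption that the cited timing makes doubtful.

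**Conclusion.** The point holds as a minor one on a secondary outcome. The single 60-day hazard ratio may understate the early relative effect. With 28-day risks of 22% and 30% and no later effect, it would be about 1.24 to 1.35 rather than 1.44, with Cox power of about 0.57 to 0.73 against 0.80 at day 28. The range depends on the later background hazard. If half of the log hazard ratio persists, Cox power is about 0.82 and there is no loss.

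All of these sizes rest on assumed rates, because the documents give none for placebo. The direction rests on the placebo-controlled timing evidence for gastrointestinal effects and fatigue, not on the open-label figures. Nothing planned is invalid.

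**What to change.** In section 4, keep the day-60 Kaplan-Meier incidence by arm and the Cox hazard ratio, and add:

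- the between-arm difference in Kaplan-Meier incidence of first adverse event, with 95% CI, at day 30 and day 60;
- the proportionality check already stated for the primary outcome, extended to the adverse-event models;
- the hazard ratio reported separately for days 0-30 and days 31-60.

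The 60-day comparison should stay because of the laboratory schedule in Table 1.

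Capture the onset date of every adverse event. Section 6.2 already requires the date of presentation, and the follow-up diary in section 3.6.5 records events, but Appendix 3 lists a start date only for serious events.

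The cost is some SAP wording, one case-report-form field and a few lines of code, with no added participants or visits. The downside is a few more safety estimates, which should be labelled descriptive.
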